6.3.2.2. Clinical Laboratory Parameters of Interest

An additional summary table of the number of participants (from the Safety Analysis Set as defined in Section 4) with "Flag Level" or "Alert Level" abnormalities for each of the clinical laboratory parameters of interest as specified in Section 3.2.2.4 will be produced. This table will summarise the number of participants with "Flag level" or "Alert level" abnormalities separately and by treatment group and placebo run-in and overall as per Section 5.2.2.

6.3.3. Vital Signs

Average of the triplicate measurements (where applicable) will be used in analyses.

Absolute values and changes from baseline in supine systolic and diastolic blood pressure and pulse rate will be summarized by treatment group and time point, according to sponsor reporting standards. Tables will be paged by parameter.

Mean changes from baseline for systolic and diastolic blood pressure and pulse rate will be plotted against time point. On each plot there will be 1 line for each treatment group with all groups on the same plot including placebo.

PFIZER CONFIDENTIAL DMB02-GSOP-RF02 8.0 *Statistical Analysis Plan Template* TMF Doc ID: 98.03 Page 38 of 61 MMRM models (as described in Section 5.2.3) will be applied to the change from baseline for supine systolic and diastolic blood pressure and pulse rate separately using the safety analysis set (as defined in Section 4). For Cohorts 1 & 2, Weeks 0 (i.e. 2-6H post-dose only), 2, 4, 6, 8 (0 and 2-6H separately), 10, 12, 16 (0 and 2-6H separately), 18, 22 and 26 (0 and 2-6H separately) assessments will be included in the model. For Cohort 3, Weeks 0 (0 and 2-6H separately), 4, 8 (0 and 2-6H separately), 12, 16 (0 and 2-6H separately), 20, 24 (0 and 2-6H separately), 28 and 32 (0 and 2-6H separately) assessments will be included. From each model, the LSMeans together with 90% confidence intervals, standard errors and p-values will be obtained for each treatment group at each time point. Differences in LSMeans between each treatment group of danuglipron relative to placebo at each time point, together with 90% confidence intervals, standard errors and 2-sided p-values will also be obtained. A plot of the LSMean differences to Placebo (including 90% confidence intervals) over time, with a separate line for each treatment group of danuglipron will be produced separately for each parameter. Standard SAS outputs will be provided to support the main statistical summary tables but will not be included in the CSR.

Maximum absolute values and maximum changes from baseline for vital signs, over all measurements taken post-dose will also be tabulated by treatment group and overall using categories as defined in the Appendix 4. Numbers and percentages of participants meeting the categorical criteria will be provided. All planned and unplanned post-dose time points will be counted in these categorical summaries. All values meeting the criteria of potential clinical concern will be listed.

Maximum decrease and increase from baseline for supine systolic and diastolic blood pressures, and maximum increase from baseline for supine pulse rate will be summarized by treatment group, according to sponsor reporting standards.

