| Suicidal ideation and behavior | The potential risk is based on the product labeling for the injectable GLP-1R agonists liraglutide and semaglutide for obesity. This risk has not been listed in the prescribing information for other marketed GLP-1R agonists for T2DM. There are no nonclinical or clinical data involving PF-06882961 to suggest an increased risk of suicidal ideation and behavior. | Suicidal ideation and behavior, along with symptoms of depression, will be monitored at every clinic visit after randomization using the C-SSRS and PHQ-9 questionnaires, with referral to a MHP for further evaluation if needed. |

| Potential Risk of Clinical Significance | Summary of Data/Rationale for Risk | Mitigation Strategy |
|--|---|--|
| Increase in HR | The potential risk is based on the product labeling for the injectable GLP 1R agonists liraglutide and semaglutide for T2DM and for obesity. Increases in HR have been noted in the clinical program with PF-06882961 with most values within the normal range. While there have been isolated vital sign values outside the reference ranges observed, in these cases the values were not considered clinically significant and there were no clinically significant adverse trends observed across dose levels, to date. | Vital signs, including HR and BP, and ECGs are assessed at all onsite study visits in all participants. |
| Acute gallbladder disease | Substantial or rapid weight loss can increase the risk of cholelithiasis. The potential risk is based on the product labeling for the injectable GLP 1R agonist liraglutide for obesity and also exenatide. In the completed clinical studies with PF-06882961, no treatment-emergent events of cholelithiasis have been observed. | Participants with symptomatic gallbladder disease are excluded from this clinical study. Participants are monitored at clinical visits for AEs and laboratory tests that may suggest development of acute gallbladder disease. |
| | Study Procedures | |
| Use of a placebo arm | Participants randomized to placebo may not experience weight loss efficacy. | A majority of the randomized study population will receive PF-06882961, and all participants will receive lifestyle counseling, which is standard of care for management of obesity. |

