7. DISCONTINUATION OF STUDY INTERVENTION AND PARTICIPANT DISCONTINUATION/WITHDRAWAL

7.1. Discontinuation of Study Intervention

It may be necessary for a participant to permanently discontinue study intervention. Reasons for permanent discontinuation of study intervention include the following:

- Criteria for a potential Hy's law case are met (see Appendix 6);
- Intent to become pregnant or pregnancy confirmed by β-hCG testing;
- Safety or tolerability concern arises, in particular if not responsive to symptomatic management, dosing with double-blind study intervention may be stopped in an individual participant at the discretion of the investigator;
- Based on mental health assessment as outlined in Section 8.2.6, should be discontinued from dosing at the discretion of the investigator.

If the criteria for permanent discontinuation are met, the site should notify the sponsor Medical Monitor or sponsor Clinician.

Note that discontinuation of study intervention does not represent withdrawal from the study. If study intervention is definitively discontinued, the participant will remain in the study to be evaluated for obesity, and will be expected to continue with all study visits and assessments as outlined in the SoA for the applicable cohort (see SoA for Cohorts 1 and 2, and SoA for Cohort 3), with the exception of dosing activities and assessment of PK. See the SoA for the applicable cohort (see SoA for Cohorts 1 and 2, and SoA for Cohort 3) for data to be collected at the time of discontinuation of study intervention and follow-up for any further evaluations that need to be completed.

In the event of discontinuation of study intervention, it must be documented on the appropriate CRF/in the medical records whether the participant is discontinuing further receipt of study intervention or also from study procedures, posttreatment study follow-up, and/or future collection of additional information.

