4. ANALYSIS SETS (POPULATIONS FOR ANALYSIS)

Data for all participants will be assessed to determine if participants meet the criteria for inclusion in each analysis population prior to unblinding and releasing the database and classifications will be documented per standard operating procedures.

Participant Analysis Set	Description
Enrolled	"Enrolled" means a participant's agreement to participate in a clinical study following completion of the informed consent process. Potential participants who are screened for the purpose of determining eligibility for the study, but do participate in the study, are not considered enrolled, unless otherwise specified by the protocol.
Randomly assigned to study intervention	All participants randomly assigned to study intervention regardless of whether or not study intervention was administered.
Evaluable	All participants randomly assigned to study intervention and who take at least 1 dose of study intervention. Participants will be analyzed according to the randomized study intervention.
Safety	All participants randomly assigned to study intervention and who take at least 1 dose of study intervention. Participants will be analyzed according to the study intervention they actually received.

Defined Analysis Set	Description
Estimand Set 1	All participants randomly assigned to study intervention and who take at least 1 dose of study intervention.For participants who discontinue study intervention, all subsequent values will be censored.
Estimand Set 2	All participants randomly assigned to study intervention and who take at least 1 dose of study intervention and do not have major protocol deviations. Major protocol deviations will be reviewed prior to database lock to identify such participants (described in Section 4.1). For participants who discontinue study intervention, all subsequent values will be censored.
PK Concentration Set	All participants randomly assigned to study intervention and who take at least 1 dose of PF-06882961 (danuglipron) and in whom at least 1 concentration value is reported.

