6.3.2.1. Focused Laboratory Summaries on Endpoints of Interest

Absolute values, changes from baseline and percent changes from baseline in calcitonin, amylase, lipase, TSH, free T4, lipid profile, liver function tests and eGFR (as outlined in Section 3.2.2.3) will be summarized by treatment group and time point as per Section 5.2.1 (unplanned readings will not be included in these summaries). Follow-up data will be including in the summaries with data from all participants in the safety analysis set. Tables will be paged by parameter.

PFIZER CONFIDENTIAL DMB02-GSOP-RF02 8.0 *Statistical Analysis Plan Template* TMF Doc ID: 98.03 Page 37 of 61 The following box and whisker plots for each parameter will be produced:

- Absolute values over time by treatment group
- Change from baseline over time by treatment group
- Percentage change from baseline over time by treatment group.

Spaghetti plots for individual data versus time, by treatment, will be produced for ALT, ALP, AST and total bilirubin:

Plots of absolute values of ALT and AST versus change from baseline in weight by treatment will also be produced.

MMRM models (as described in Section 5.2.3) will be applied to the change from baseline at Weeks 4, 8, 12, 16, 22 and 26 (as applicable) for Cohorts 1 & 2 and at Weeks 4, 8, 12, 16, 20, 24, 28 and 32 for Cohort 3 separately and for each parameter separately using the safety analysis set (as defined in Section 4). For ALT, AST, alkaline phosphatase and GGT, the MMRM models will instead be applied to the change from baseline on the natural log scale and the MMRM results will be back-transformed for reporting, similar to the primary endpoint as described in Section 6.1.1.1.

From each model, the LSMeans together with 90% confidence intervals, standard errors and p-values will be obtained for each treatment group at each time point. Differences in LSMeans between each treatment group of danuglipron relative to placebo at each time point, together with 90% confidence intervals, standard errors and 2-sided p-values will also be obtained. A plot of the LSMean differences to Placebo (including 90% confidence intervals) over time, with a separate line for each treatment group of danuglipron will be produced separately for each parameter. Standard SAS outputs will be provided to support the main statistical summary tables but will not be included in the CSR.

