6.3.4. Electrocardiograms

Average of the triplicate measurements (where applicable) will be used in analyses. Absolute values and changes from baseline in QT, heart rate, QTcF, PR and QRS will be summarized by treatment group and time point using sponsor reporting standards. Tables will be paged by parameter.

Mean changes from baseline in QT, heart rate and QTcF will be plotted against time point. On each plot there will be 1 line for each treatment group with all treatments included on the same plot including placebo.

MMRM models (as described in Section 5.2.3) will be applied to the change from baseline at Weeks 2, 4, 6, 8, 10, 12, 16, 18, 22 and 26 for Cohorts 1 & 2 and at Weeks 4, 8, 12, 16, 20, 24, 28 and 32 for Cohort 3 separately, for QT, heart rate and QTcF separately using the safety analysis set (as defined in Section 4). From each model, the LSMeans together with 90% confidence intervals, standard errors and p-values will be obtained for each treatment group at each time point. Differences in LSMeans between each treatment group of danuglipron relative to placebo at each time point, together with 90% confidence intervals, standard errors and 2-sided p-values will also be obtained. A plot of the LSMean differences to Placebo (including 90% confidence intervals) over time, with a separate line for each treatment group of danuglipron will be produced separately for each parameter. Standard SAS outputs will be provided to support the main statistical summary tables but will not be included in the CSR.

PFIZER CONFIDENTIAL DMB02-GSOP-RF02 8.0 Statistical Analysis Plan Template TMF Doc ID: 98.03 Page 39 of 61 ECG endpoints and changes from baseline (QTcF, PR and QRS) will also be summarized descriptively by treatment group and overall using categories as defined in the Appendix 4 (for QTc these correspond to the Pfizer Guidance¹⁰). Numbers and percentages of participants meeting the categorical criteria will be provided. All planned and unplanned post-dose time points will be counted in these categorical summaries. All values meeting the criteria of potential clinical concern will be listed.

Maximum absolute value (post-dose) and the maximum increase from baseline for QTcF, PR and QRS will be summarized by treatment group according to sponsor reporting standards.

Listings of participants with any single post-dose value > 500 msec will also be produced for QTcF.

6.3.5. Assessment of mental health as determined by C-SSRS and PHQ-9.

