6.4.6. CFB in systolic and diastolic BP over time

In all cases a dataset similar to Estimand Set 1 as specified in Section 4 will be utilised.

Absolute and change from baseline in systolic and diastolic blood pressure will be summarised descriptively and analyzed as described in Section 6.3.3 at Weeks 2, 4, 6, 8,

10, 12, 16, 18, 22 and 26 for Cohorts 1 & 2 and at Weeks 4, 8, 12, 16, 20, 24, 28 and 32 for Cohort 3 separately.

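### The mean-change models for pulse rate, ECG parameters and the non-lipid safety labs include readings taken after study drug is stopped, so they can understate an effect that is present only on drug

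*SAP*

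**What the plan says.** Three groups of safety models share one data set. SAP Section 6.3.3 models blood pressure and "pulse rate separately using the safety analysis set (as defined in Section 4"). Section 6.3.4 fits its models "for QT, heart rate and QTcF separately using the safety analysis set (as defined in Section 4"). Section 6.3.2.1 models calcitonin, amylase, lipase, TSH, free T4, lipids, liver tests and eGFR, "for each parameter separately using the safety analysis set (as defined in Section 4").

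SAP Section 4 defines the Safety set as everyone randomized who took at least one dose, and adds: "Participants will be analyzed according to the study intervention they actually received". It has no rule about values after drug is stopped. Estimand Sets 1 and 2, in the same section, do have one: everything after discontinuation is censored. SAP Section 5.3 speaks of censoring only for efficacy data.

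Protocol Section 7.1 says that after stopping study drug "the participant will remain in the study to be evaluated for obesity, and will be expected to continue with all study visits". Only dosing activities and PK are dropped.

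Two safety-related measures get a second analysis with off-drug values removed. SAP Section 6.4.6 (blood pressure) states: "In all cases a dataset similar to Estimand Set 1 as specified in Section 4 will be utilised". Section 6.4.7 (lipids) says the same.

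**The concern.** Put together, these rules mean that vital signs, ECGs and chemistry from participants no longer taking the drug are expected at the modelled weeks, and that they count toward the arm they were assigned to. If a drug effect fades once dosing stops, those readings pull the arm mean toward placebo.

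This matters most where the effect is a named risk. Protocol Section 2.3.1 lists increase in heart rate and notes: "Increases in HR have been noted in the clinical program with PF-06882961 with most values within the normal range". It relies on amylase and lipase to monitor for pancreatitis, and on creatinine and eGFR for renal function. For a safety measure, dilution errs toward reassurance. The trial is also meant to inform dose selection. If stopping differed between arms, the dilution would differ too, and the dose trend in these means would be distorted. Protocol Section 4.2 does not permit downward titration and says that participants who cannot tolerate their scheme or dose may have to stop, so a difference between arms is plausible, though not documented.

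**Working it through.** **Do off-drug readings enter?**
1. Data set: Safety set (SAP 6.3.2.1, 6.3.3, 6.3.4).
2. Censoring in that set: none (SAP 4). The rule on treatment actually received settles which arm a participant counts in, not when their data stop counting.
3. Censoring elsewhere: SAP 5.3 covers efficacy data only. SAP 5.2.3 mentions censoring as one cause of missing values, but sets no rule for safety data.
4. Collection: all visits and assessments continue off drug except dosing and PK (Protocol 7.1 and the notes to both Schedules of Activities).

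So they enter. One part is largely exempt. The pulse-rate model has separate 2-6 hour post-dose time points (Weeks 0, 8, 16 and 26 in Cohorts 1 and 2; Weeks 0, 8, 16, 24 and 32 in Cohort 3). A participant who is not dosing should have no such reading. The direct effect is therefore at the pre-dose time points, which include all scheduled ECGs.

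**The plan's only stopping figure.** Protocol Section 9.2 assumes 25% drop-out (Cohorts 1 and 2) or discontinuation (Cohort 3). Its completer counts reproduce: 420 × 0.75 = 315; 60 × 0.75 = 45; 67 × 0.75 = 50.25 (stated as about 50); 34 × 0.75 = 25.5 (about 25); 112 × 0.75 = 84. This is an overall non-completion rate. It does not separate stopping drug from leaving the study, and it is not given by arm.

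**Dilution.** Let d be the share of an arm that has stopped drug by the visit, r the share of stoppers still measured, and c the share of the effect that persists off drug. The fraction of the on-drug effect left in the arm mean of measured participants is

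[(1 − d) + c·d·r] / [(1 − d) + d·r].

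The model estimate will be close to this but not identical, because it also uses earlier visits and baseline. With d = 25% and c = 0:
- r = 1: 0.75 / 1.00 = 75%
- r = 0.5: 0.75 / 0.875 = 86%
- r = 0: 0.75 / 0.75 = 100%

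The range over other assumed values:

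| d | c = 0, r = 1 | c = 0, r = 0.5 | c = 0.5, r = 1 | any c, r = 0 |
|---|---|---|---|---|
| 10% | 90% | 95% | 95% | 100% |
| 25% | 75% | 86% | 88% | 100% |
| 40% | 60% | 75% | 80% | 100% |

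As an illustration, an assumed on-drug rise of 5 bpm with c = 0 and d = 25% would read 3.75 bpm (r = 1), 4.29 bpm (r = 0.5) or 5 bpm (r = 0). Apart from the 25%, every input here is an assumption, and using 25% for d is itself one.

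**The case against.** **The size is not documented, and this stands.** A reader might infer that the heart-rate and laboratory risks will be diluted, and most so at the highest doses. The documents give no stopping rate by arm, no retention after stopping and no evidence of reversal off drug for any of these measures. It is easy to build a striking example: if 10% of low-dose and 40% of high-dose readings were off drug, true rises of 3 and 6 bpm would read 2.7 and 3.6, shrinking the gap from 3.0 to 0.9. But with half of stoppers re-measured, 40% of readings off drug would need about 57% of the arm to stop (0.57 × 0.5 / (0.43 + 0.57 × 0.5) = 0.40). Nothing supports such a figure.

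**Using the safety set is conventional, and this stands.** Protocol Section 3 gives the safety endpoints no estimand. Blood pressure and lipids get a censored version because they are also tertiary endpoints with their own objective. The absence of one for pulse rate is a design distinction, not an error. An all-data view also has value for delayed effects.

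**Other outputs detect these risks, and this stands.** Maximum pulse-rate and QTcF summaries, categorical tables, laboratory flag and alert counts (SAP 6.3.2.2) and tiered adverse events are not averaged down. Adverse events also have an interval ending two days after last dose (SAP 3.2.2.1.2). A reader who infers that a signal would go unseen goes too far. Means are also reported at every visit, so earlier visits with fewer stoppers can be inspected.

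**Post-dose pulse readings are protected, which stands in part.** Post-dose and pre-dose values share one model, so a missing post-dose value is implicitly predicted from correlated readings that may be off drug.

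**Censoring has its own bias, and this stands.** If those with the largest effects stop, the censored model depends on missing at random for them.

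None of this removes the gap: pulse rate, ECG heart rate and the non-lipid labs have no model-based estimate restricted to time on drug.

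**Conclusion.** The point holds as a possible dilution. The safety-set models for pulse rate, QT/heart rate/QTcF and the non-lipid labs will include off-drug readings, mainly at pre-dose time points. Any effect that reverses off drug can be understated, by more in arms where more participants stop drug but remain in the study.

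The size cannot be taken from the documents. With 25% stopped and full reversal assumed, between 75% and 100% of the effect is left, depending on how many stoppers are re-measured. Partial persistence reduces the loss further.

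The point does not extend to lipids or blood pressure, which already have censored versions, or to the maximum-value, categorical and flag/alert tables. QTcF is modelled in the same way but is not a listed risk in Protocol Section 2.3.1. The primary body-weight analysis is unaffected, since it uses Estimand Set 1. This is an inexpensive improvement to how a named risk is described, not a correction of an invalid analysis.

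**What to change.** Keep the safety-set models. In SAP Sections 6.3.2.1, 6.3.3 and 6.3.4, add the same models with values after discontinuation of study drug censored, using the Estimand Set 1 rule. Cover at least pulse rate, ECG heart rate, amylase, lipase and eGFR; QTcF is optional. Alongside both versions, tabulate the number of participants on and off drug at each visit by arm, so that the possible dilution can be judged from the data. Describe the on-drug effect from the censored models, and keep the all-data models for the full picture.

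The cost is a few lines of SAP text and a rerun of existing programs with a censoring rule the SAP already has and already applies to blood pressure and lipids. The downsides are more tables, and that the added models rely on missing at random, as the primary analysis does.

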- Physical examination: Complete physical examination performed according to the SoA, with height measured at V1 only. A limited physical examination is performed at follow-up V20 and may be performed at non-specified visits if there are findings during the previous exam or new/open AEs, if appropriate and at investigator discretion. Ŧ
- **Body weight:** The second weight measurement should be obtained at least 1-2 minutes apart from the first weight measurement. ьio
- Supine vital signs (BP and pulse rate): At V3, V7, V11, V15 and V19, triplicate vital signs will be measured pre-dose and triplicate vital signs will be measured 1 time within the window of approximately 2-6 hours post-dose (around the same time as post-dose PK samples are collected and according to the chronology in Appendix 9). Ъ.
- Eating-Related Factors Daily Diary: Only participants at selected US sites will complete this PRO diary, which will be done daily at home on a handheld device.
- Dosing diary review: For telephone visits, this review consists of site staff reminding participants to record doses taken as well as any missed doses in their dosing diary and to bring the diary to in-clinic study visits. For onsite visits, site staff should review the returned dosing diary entries with participants.
- Study intervention: For V2 only, study intervention reflects single blinded placebo. For V3, V5, V7, V9, V11, V13, V15 and V17, study intervention is dispensed via IRT and reflects double-blinded randomized PF-06882961 or placebo. 7
- Pregnancy tests: Serum and urine pregnancy tests are required for all females regardless of childbearing potential. For the on-site urine pregnancy tests performed at each planned in-clinic visit V2 through V20, the test result must be negative in order to continue participation in the study.

- **PK sampling:** At V3, V7, V11, V15 and V19, PK samples will be collected pre-dose *and* 1 time within the window of approximately 2-6 hours *post-dose* (around the same time as post-dose vital sign measurements and according to the chronology in Appendix 9). Ħ.
 - Banked biospecimen Prep D1: If not collected on the designated collection day, collect at the next available time point when biospecimens are being collected in conjunction with a participant visit. 'n.

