8.2.2. Vital Signs

8.2.2.1. Blood Pressure and Pulse Rate

In this study, assessment of vital signs (systolic BP, diastolic BP, and pulse rate) will occur at the nominal time points specified in the SoA for the applicable cohort (see SoA for Cohorts 1 and 2, and SoA for Cohort 3) per the following specifications:

- At V1, the participant's arm circumference should be measured (eg, using an anthropometric tape) at the midpoint of the length of the upper arm and the appropriate cuff selected and used throughout the study.
- BP and pulse rate will be measured via an automated device using an oscillometric method (not auscultation).

- Assessment of BP and pulse rate can be manual (rather than using an automated device), only if an automated device is not available; however, when done manually pulse rate must be measured in the brachial/radial artery for at least 30 seconds.
- Supine BP and pulse rate will be measured with the participant's arm supported at the level of the heart, following a rest of at least 5 minutes and BP will be recorded to the nearest mm Hg. Triplicate assessments will be measured, with an interval of at least 1-2 minutes between each measurement, and these will be performed pre-dose (as applicable) at each planned in-clinic study visit. For visits with post-dose PK collections as specified in the SoA for the applicable cohort (see SoA for Cohorts 1 and 2, and SoA for Cohort 3), these triplicate assessments will also be performed 1 time within the window of approximately 2-6 hours post-dose (around the same time as post-dose PK samples are collected and according to the chronology in Appendix 9). Each triplicate reading will be recorded, and the average of the 3 measurements at V3 (Day 1) will serve as the participant's baseline.
- Same arm (preferably the dominant arm) will be used for BP and pulse rate assessments throughout the study, whenever possible.
- Participants should be instructed not to speak during BP and pulse rate measurements.
- See Appendix 9 for proposed chronology of procedures for nominal time points when vital sign assessments coincide with other procedures.

Additional collection times, or changes to collection times of BP and pulse rate will be permitted, as necessary, to ensure appropriate collection of safety data.

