3. ENDPOINTS AND BASELINE VARIABLES: DEFINITIONS AND CONVENTIONS

For all endpoints, unless otherwise specified below, baseline is defined as the result closest prior to dosing at V3 (Day 1).

The "End of Treatment" definition is applied at the endpoint level (not the subject-level) and is defined for relevant endpoints as Week 26 for Cohorts 1 & 2, and as Week 32 for Cohort 3.

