3.2.2.1. Vital Signs

Vital sign measurements (blood pressure and pulse rate) will be taken as detailed in the Schedule of Activities given in the protocol. The average of the triplicate measurements collected at each appropriate assessment time will be calculated for each vital sign parameter.

Baseline will be defined as the average of the triplicate measurements at the visit closest prior to dosing at Visit 3 (Day 1).

Changes from baseline for supine systolic and diastolic blood pressure and pulse rate will be calculated for each post baseline measurement.

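### SAP 6.3.3 enters the Cohort 3 Day 1 pre-dose reading, which is the baseline itself, as an outcome in the change-from-baseline MMRMs for blood pressure and pulse rate, so the first-choice unstructured fit fails

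*SAP*

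**What the plan says.** SAP 6.3.3 (Vital Signs) applies the MMRM of SAP 5.2.3 to change from baseline in supine systolic pressure, diastolic pressure and pulse rate, each separately, on the safety analysis set. The two visit lists stand in consecutive sentences:

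- Cohorts 1 and 2: "For Cohorts 1 & 2, Weeks 0 (i.e. 2-6H post-dose only), 2, 4, 6, 8 (0 and 2-6H separately" and so on.
- Cohort 3: "For Cohort 3, Weeks 0 (0 and 2-6H separately), 4, 8 (0 and 2-6H separately" and so on.

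The section then asks for "Differences in LSMeans between each treatment group of danuglipron relative to placebo at each time point, together with 90% confidence intervals", with standard errors and p-values.

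Three places define the baseline. SAP 3.2.2.1 (Vital Signs): "Baseline will be defined as the average of the triplicate measurements at the visit closest prior to dosing at Visit 3 (Day 1". SAP 3, for endpoints generally: "baseline is defined as the result closest prior to dosing at V3 (Day 1". Protocol 8.2.2.1: "the average of the 3 measurements at V3 (Day 1) will serve as" the baseline. The vital-signs footnote to the Cohort 3 schedule (protocol 1.3.2) plans a single pre-dose triplicate at V3: "At V3, V7, V11, V15 and V19, triplicate vital signs will be measured pre-dose and triplicate vital signs will be measured 1 time" after the dose. SAP 3.2.2.1 also says that changes are derived for post-baseline readings.

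SAP 5.2.3 makes an unstructured covariance the first choice. If convergence or fit is poor, it allows other structures but names none.

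**The concern.** For Cohort 3 the Week 0 reading at 0H is the baseline, so its change from baseline is baseline minus baseline. The model is asked to estimate a variance, and 13 covariances with the other time points, for an outcome that is constant at zero. The Cohorts 1 and 2 sentence avoids this by restricting Week 0 to the post-dose reading; the Cohort 3 sentence does not.

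The planned fit then breaks down, and the choice of replacement is left open. Some replacements run without complaint but treat a constant as data.

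The models at stake are the three Cohort 3 vital-sign MMRMs. They are the only planned models of the 2-6 hour post-dose readings, of vital-sign pulse rate, and of blood pressure on the safety set in that cohort. Protocol 2.3.1 lists increased heart rate as a potential risk.

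**Working it through.** The documents give no figure to reproduce here, and no SDs for vital signs. Where an SD is needed it is assumed, and a range is shown.

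**Inputs**

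- Cohort 3 time points (SAP 6.3.3): Week 0 (0H, 2-6H), 4, 8 (×2), 12, 16 (×2), 20, 24 (×2), 28, 32 (×2) = 2+1+2+1+2+1+2+1+2 = 14.
- Cohort 3 size (protocol 9.2): 16 + 3 × 32 = 112, with up to about 140 permitted, and 25% discontinuation assumed.
- Fixed effects (SAP 5.2.3): treatment by time, baseline by time, and sex. The sex term has no interaction with time.

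**1. The row is zero.** Change at Week 0 0H = (V3 pre-dose mean) − (V3 pre-dose mean) = 0. If the V3 pre-dose triplicate is missing, baseline comes from an earlier visit and the 0H row is missing too, so every observed value is still zero. The one exception is an unplanned later pre-dose repeat, which protocol 8.2.2.1 allows: "Additional collection times, or changes to collection times of BP and pulse rate will be permitted, as necessary".

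**2. The unstructured fit has no maximum.** Let v be the 0H variance. As v falls to zero, the REML log-likelihood contains −(n − 6)/2 × ln v. The 6 counts the parameters pinned by that row: four arm means, the baseline slope and the shared sex coefficient. Each tenfold cut in v therefore adds:

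- n = 112: (106/2) × ln 10 = 53 × 2.3026 = 122.0
- n = 140: (134/2) × ln 10 = 67 × 2.3026 = 154.3

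There is no limit to this, and neither figure depends on an assumed SD. A simulated Cohort 3 (16/32/32/32, complete data, assumed SD 12, correlation 0.5) agrees. With v = 1, 10⁻², 10⁻⁴, 10⁻⁶ and 10⁻⁸, −2 REML was 7804, 7315, 6827, 6339 and 5851. That is a fall of about 488 per hundredfold cut, equal to 2 × 2 × 122.0. The residual covariance had rank 13 of 14. The sex coefficient was forced from 1.20 (SE 1.24, row removed) to 3 × 10⁻¹⁰, so the stratum adjustment is in effect switched off.

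**3. The treatment contrast under the planned structure.** The other 13 rows' covariance was held at its true value and v set to 10⁻⁴ (300 replicates, sex effect 3, three SD pairs). The mean absolute shift in the Week 32 200 mg versus placebo contrast was 0.008-0.014 SE with complete data and 0.022-0.035 SE with 25% dropout. The SE ratio was 1.000.

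**4. The fallback.** A structure with time-specific variances fails as in step 2. A homogeneous-variance structure converges, but spreads almost the same residual sum of squares over one more row per participant:

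- Complete data: SE ratio ≈ √(13/14) = 0.964.
- With 25% dropout, a mean of 11.375 real rows per participant: √(11.375/12.375) = 0.959.

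REML fits with and without the zero row used 60 replicates per setting and assumed between/within SD pairs 8/6, 12/6, 12/9, 6/8, 15/5 and 4/10:

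| Structure | SE ratio, complete | SE ratio, 25% dropout |
|---|---|---|
| Compound symmetry | 0.964 for all six pairs | 0.958-0.959 |
| AR(1) | 0.957-0.963 | 0.951-0.958 |

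Later pre-dose repeats in 1, 3 or 6 of 112 participants (SD pair 8/6, complete data) leave the compound-symmetry ratio at 0.964, 0.965 and 0.966.

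**5. Output without content.** At 0H: (4 LSMeans + 3 differences) × 3 parameters = 21 rows.

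**6. With the row removed.** Thirteen time points remain, with 13 × 14/2 = 91 covariance parameters instead of 14 × 15/2 = 105. In the simulated data of step 2 the matrix is full rank (smallest eigenvalue 32.8) and −2 REML is finite at 7776.

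**The case against.** The strongest reply is that this is a slip in a visit list, with the right wording one sentence earlier, and that it cannot fail unnoticed. A model with no finite maximum would send the programmer to the data, where a column of zeros is obvious. The 4% shrinkage in standard errors then needs two further choices that the SAP does not make: a homogeneous structure, and keeping the zeros after seeing them.

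Most of that stands. The shrinkage is conditional, and the harm is a failed planned fit followed by an unspecified repair. But dropping the row would be an undocumented departure from explicit SAP text, and SAP 5.2.3 points towards changing the covariance rather than the visit list.

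Failure also requires every observed 0H change to be zero. In single trial fits with an assumed repeat-difference SD of 5, later pre-dose repeats in 1, 3 or 6 of 112 participants let the unstructured model converge, with 0H variances of about 0.005, 0.12 and 0.90. That condition is accepted. It still leaves a time point made up almost entirely of zeros.

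Partial substitutes exist. SAP 6.4.6 models systolic and diastolic pressure from Week 4, but on a dataset like Estimand Set 1 and with no post-dose readings listed. SAP 6.3.4 models ECG heart rate on the safety set from Week 4, which is close to pre-dose pulse rate. The descriptive, categorical and maximum-change summaries are untouched. SAP 5.1 rules out formal testing outside the primary and the efficacy-related endpoints, and SAP 6.3.1, writing about adverse events, calls safety analysis generally exploratory. These points lower the stakes; they do not make the visit list correct.

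**Conclusion.** The concern holds. As written, the Cohort 3 list in SAP 6.3.3 gives one of 14 time points an outcome that is zero by definition, and the first-choice unstructured fit has no finite REML maximum. This follows from the baseline definition and needs no assumed SD. It is conditional only on there being no later pre-dose repeat on Day 1.

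If a homogeneous fallback keeps the zeros, standard errors are 3.6% too small under compound symmetry with complete data and up to 4.9% too small under AR(1) with 25% dropout, across the assumed SD pairs. No material bias in the treatment contrasts is claimed.

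The scope is three Cohort 3 safety models. The primary endpoint, Cohorts 1 and 2, the ECG models and the summary tables are not affected. It should be fixed because the text is wrong as it stands and the correction is immediate.

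**What to change.** In SAP 6.3.3, restrict Week 0 for Cohort 3 to the 2-6 hour post-dose reading, with the same qualifier the paragraph uses for Cohorts 1 and 2, and leave the rest of the Cohort 3 list unchanged. That leaves 13 outcome time points. The Cohorts 1 and 2 wording is the support for keeping the Week 0 post-dose reading. SAP 6.3.4 and 6.4.6 list no Week 0 for Cohort 3, so they agree with dropping 0H but do not settle the post-dose reading.

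The cost is one phrase in the SAP. Data collection does not change and no information is lost, because the baseline value is already in the model as a covariate.
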